2. PROTOCOL CHANGES DETAILS

Amendments to the protocol are detailed below, except for editorial changes and minor clarification changes. If it is necessary to clarify the edits, newly added text is identified using in blue and deleted text is identified by strikethrough, red font.

Protocol Section	Text in Version 7.0 (Amendment 6-COL)	Changes through Version 8.0 (Amendment 7-COL)	Rationale for Change
Section 7.5.5	(Paragraph 3) Subjects who undergo a solid organ (including kidney), hematopoietic stem cell, or bone marrow transplantation will have their study medication (vadadustat or darbepoetin alfa) permanently discontinued.	(Paragraph 3) Subjects who undergo a solid organ (including kidney), hematopoietic stem cell, or bone marrow transplantation will have their study medication (vadadustat or darbepoetin alfa) permanently discontinued. See Section 9.4, Study Medication Stopping Rules for additional details on the management of subjects with ALT and AST abnormalities.	To include a reference to Study Medication Stopping Rules for management of subjects with ALT and AST abnormalities.
Section 9.4 (added)		Study Medication Stopping Rules Study medication must be permanently discontinued if a subject meets one of the criteria in Table 2 below Table 1. Study Medication Stopping Rules See Section 10.1.1, Adverse Events for reporting requirements related to a subject being permanently discontinued based on meeting the laboratory abnormalities list above in Table 2.	To include a table of liver function test results that would require permanent discontinuation of vadadustat.

		
ALT or AST >3x ULN and total bilirubin >2x ULN
 
ALT or AST >3x ULN and INR >1.5
 
ALT or AST >8x ULN
 
ALT or AST remains >5x ULN over 2 weeks*
 
ALT or AST >3x ULN with symptoms including e.g., fatigue, nausea, vomiting, right upper quadrant pain, fever, rash or eosinophilia
	
Permanently Discontinue Treatment
 
Permanently Discontinue Treatment
 
Permanently Discontinue Treatment
 
Permanently Discontinue Treatment
 
Permanently Discontinue Treatment
	

Section 10.1.1
	
(paragraph 8)
 
Abnormalities in ALT, AST and Total Bilirubin - Abnormalities in ALT, AST and Total Bilirubin should be reported to the Sponsor’s Medical Monitor or CRO designee within 24 hours of awareness as SAE with “medical significance” criteria selected, if the following conditions are met:
 
 • New elevation in ALT or AST > 3 times ULN, with or without an elevation of total serum bilirubin > 2 times ULN; AND • No other reason was identified that explains the increased ALT/AST with or without an increased 	
(paragraph 8)
 
Abnormalities in ALT, AST and Total Bilirubin - Abnormalities in ALT, AST and Total Bilirubin should be reported to the Sponsor’s Medical Monitor or CRO designee within 24 hours of awareness as SAE with “medical significance” criteria selected, if the following conditions are met:
 
 • New elevation in ALT or AST > 3 times ULN, with or without an elevation of total serum bilirubin > 2 times ULN; AND • No other reason was identified that explains the increased ALT/AST with or without an increased bilirubin (eg, viral hepatitis, acute liver disease). 	
To include language for elevations in ALT or AST >3 times ULN.
	

	
bilirubin (eg, viral hepatitis, acute liver disease).
 
If new elevations in ALT or AST > 3 times ULN, with or without an elevation of total serum bilirubin > 2 times ULN are identified, the following steps are to be taken:
 
 • Temporary discontinuation of Investigational Medicinal Product (IMP); • Repeat testing of ALT, AST, ALP and total bilirubin, to be completed within 48 to 72 hours to confirm the abnormalities and to determine trend; • IMP should not be resumed until monitoring indicates abnormalities have resolved or have stabilized. 	
If new elevations in ALT or AST > 3 times ULN, with or without an elevation of total serum bilirubin > 2 times ULN are identified, the following steps are to be taken:
 
 • Temporary discontinuation of Investigational Medicinal Product (IMP); • Repeat testing of ALT, AST, ALP, and total bilirubin, to should be completed within 48 to 72 hours to confirm the abnormalities and to determine trend; • IMP should not be resumed until monitoring indicates abnormalities have resolved or have stabilized. 
Details on the management of subjects with other ALT and AST abnormalities are further described in Section 9.4, Study Medication Stopping Rules.
	
Section 10.1.2	
(paragraph 2)
 
In addition to the above criteria for classifying AEs as serious, the following situations will also be classified as serious for purposes of this study:
 
 • Dialysis or Transplantation - Events requiring transition to chronic, ongoing dialysis, or requiring an acute transient course of dialysis, or requiring an immediate kidney transplantation (ie, not pre-planned) will be classified as serious. Guidance for the reporting of these events is provided in Section 10.1.1, Adverse Events. • Malignancies – Newly diagnosed malignancies or a recurrence of a 	
(paragraph 2)
 
In addition to the above criteria for classifying AEs as serious, the following situations will also be classified as serious for purposes of this study:
 
 • Dialysis or Transplantation - Events requiring transition to chronic, ongoing dialysis, or requiring an acute transient course of dialysis, or requiring an immediate kidney transplantation (ie, not pre-planned) will be classified as serious. Guidance for the reporting of these events is provided in Section 10.1.1, Adverse Events. • Malignancies – Newly diagnosed malignancies or a recurrence of a malignancy should be reported as an SAE with the seriousness criterion “medically important” if no other seriousness criteria are met. If a subject develops basal cell carcinoma of skin, squamous cell carcinoma, or cervical carcinoma in situ during the study, or has worsening of these 	
To define a list of designated medical events that shall always be classified as serious adverse events (SAEs).

	
malignancy should be reported as an SAE with the seriousness criterion “medically important” if no other seriousness criteria are met. If a subject develops basal cell carcinoma of skin, squamous cell carcinoma, or cervical carcinoma in situ during the study, or has worsening of these events from Baseline, the Investigator will determine if the event is reported as an AE or SAE.
	
events from Baseline, the Investigator will determine if the event is reported as an AE or SAE.
 
• Designated Medical Events - The sponsor maintains a list of designated medical events (DME) that they will always classify as serious adverse events. If an event on the DME list is reported as an AE additional information on the event (e.g. investigator confirmation of seriousness, causality) will be requested from the Investigator.	
--	--	--	--

---

## Statistical Analysis Plan AKB-6548-CI-0014 and AKB-6548-CI-0015

## Abbreviations

| Abbreviation | Definition                              |
|---------------------|--|
| AE                  | adverse event                                  |
| AESI                | adverse events of special interest             |
| ALT                 | alanine aminotransferase                       |
| ANCOVA              | analysis of covariance                         |
| AST                 | aspartate aminotransferase                     |
| CBC                 | complete blood count                           |
| CHF                 | congestive heart failure                       |
| CKD                 | chronic kidney disease                         |
| CRF                 | case report form                               |
| CRP                 | c-reactive protein                             |
| CSR                 | clinical study report                          |
| CTCAE               | Common Terminology Criteria for Adverse Events |
| DA                  | darbepoetin alfa                               |
| DBP                 | diastolic blood pressure                       |
| DD                  | dialysis dependent                             |
| ECG                 | electrocardiography                            |
| eCRF                | electronic case report form                    |
| eGFR                | estimated glomerular filtration rate           |
| Epo                 | erythropoietin                                 |
| EpoA                | erythropoietin alfa                            |
| EOS                 | end of study                                   |
| EOT                 | end of treatment                               |
| ESA                 | erythropoietin-stimulating agent               |
| EU                  | European Union                                 |
| FAS                 | Full Analysis Set                              |
| FCS                 | fully conditional specification                |
| Hb                  | hemoglobin                                     |
| HDL                 | high-density lipoprotein                       |
| HLGT                | high-level group term                          |
| HLT                 | high-level term                                |
| HR                  | hazard ratio                                   |
| IDMC                | Independent Data Monitoring Committee          |
| IV                  | intravenous                                    |

## Statistical Analysis Plan AKB-6548-CI-0014 and AKB-6548-CI-0015

| Abbreviation | Definition                             |
|---------------------|---|
| IWR                 | interactive web response                      |
| LDL                 | low-density lipoprotein                       |
| LLD                 | lower limits of detection                     |
| MACE                | major adverse cardiovascular event(s)         |
| MAR                 | missing at random                             |
| MNAR                | missing not at random                         |
| MMRM                | mixed models for repeated measurements        |
| MedDRA              | Medical Dictionary for Regulatory Activities  |
| NDD-CKD             | non-dialysis-dependent chronic kidney disease |
| NEC                 | not elsewhere classified                      |
| NYHA                | New York Heart Association                    |
| PEP                 | primary efficacy period                       |
| PK                  | pharmacokinetic                               |
| PP                  | per protocol                                  |
| PT                  | preferred term                                |
| RBC                 | red blood cell                                |
| ROW                 | Rest of World                                 |
| SAE                 | serious adverse event                         |
| SAP                 | statistical analysis plan                     |
| SBP                 | systolic blood pressure                       |
| SC                  | subcutaneous                                  |
| SD                  | standard deviation                            |
| SEP                 | secondary efficacy period                     |
| SMQ                 | Standardized MedDRA Query                     |
| SOC                 | system organ class                            |
| TEAE                | treatment-emergent adverse event              |
| TIBC                | total iron-binding capacity                   |
| TSAT                | transferrin saturation                        |
| uACR                | urine albumin-to-creatinine ratio             |
| ULN                 | upper limit of normal                         |
| US                  | United States                                 |
| VEGF                | vascular endothelial growth factor            |
| WBC                 | White blood cells                             |

## 1 INTRODUCTION

This statistical analysis plan (SAP) covers the two PRO2TECT studies, Protocols AKB-6548-CI-0014 and AKB-6548-CI-0015, hereafter referred to as CI-0014 and CI-0015, respectively.

The SAP supports the Statistical Methods Section of the clinical study reports (CSRs). It elaborates upon the protocol-specified endpoint definitions and the formal statistical methods that will be used in analyzing both studies. Unless otherwise specified, all analyses will be conducted for each study separately.

Throughout this SAP, planned analyses of both studies are identical to each other except in those places that specifically identify where the plans diverge. Akebia does not intend to pool data together for formal efficacy and general safety analyses; however, analyses of major adverse cardiovascular events (MACE) will be pooled from both studies. A separate SAP will describe the planned methodology for the MACE analyses.

If the analyses described in the protocols differ from those in this SAP, the methods of the SAP prevail.

This SAP contains language and programming code that specifies the exact intent of each analysis. The sponsor will finalize and sign this document prior to locking the database and unblinding (see [Section 2.5](#)). Many of the analyses described in this SAP are quite complex. A blinded team of clinicians and statisticians will review the data carefully to develop conventions and analytic methods not anticipated in writing this SAP.

## 2 DESCRIPTION OF THE STUDIES

Both PRO2TECT studies are Phase 3, randomized, open-label, active-controlled trials of the efficacy and safety of vadadustat compared to darbepoetin alfa (DA). CI-0014 addresses the correction of anemia and maintenance of hemoglobin (Hb) in subjects with anemia secondary to non-dialysis-dependent chronic kidney disease (NDD-CKD). CI-0015 addresses the maintenance treatment of anemia after conversion from current erythropoietin-stimulating agent (ESA) therapy in subjects with anemia secondary to NDD-CKD.

### 2.1 Randomization and Stratification

In each study, subjects who meet all inclusion and no exclusion criteria are randomized 1:1 to vadadustat or darbepoetin alfa. Randomization is stratified by the following three variables:

- Geographic region: United States (US); European Union (EU); Rest of World (ROW)
- New York Heart Association (NYHA) congestive heart failure (CHF) class: 0 or I; II or III

In addition, each study has the following strata defined by Hb levels at entry:

|                      |  |                                       |
|----------------------|--|---------------------------------------|
| Study entry Hb level | CI-0014
<9.5 g/dL; ≥9.5 g/dL | CI-0015
<10 g/dL; ≥ 10 g/dL |
|----------------------|--|---------------------------------------|

## 2.2 Study Periods

Following randomization, the studies have the following initial study periods:

### *Study CI-0014*

- **Correction Period (Weeks 0 to 23):** initial period on study medication for correction of Hb
- Maintenance Period (Weeks 24 to 52):
  - Weeks 24 to 36: primary efficacy period (PEP)
  - Weeks 40 to 52: secondary efficacy period (SEP)

### *Study CI-0015*

- Conversion and Maintenance Period (Weeks 0-52):
  - Weeks 0 to 23: conversion to study treatment for maintaining Hb
  - Weeks 24 to 36: PEP
  - Weeks 40 to 52: SEP

After Week 52, subjects in both studies will proceed to the following 2 periods:

- **Long-Term Treatment Period (Weeks 53-End of Treatment [EOT]):** continued treatment with study medication to assess long-term safety
- **Follow-up Period (EOT + 4 weeks):** post-treatment visit (either in person or by telephone) to assess safety

The duration of the trial will depend on how long it takes for a total of 631 adjudicated MACE to occur in the 2 studies combined. A separate SAP will describe the planned MACE analyses, including the method planned for pooling data from the 2 PRO2TECT studies.

The safety reporting period for a subject enrolled in this study begins upon randomization and ends at the final protocol-required study contact (visit or telephone), also known as a subject's end of study (EOS). In addition, the Investigator should report any adverse event (AE) that occurs after this period if he or she assesses it as possibly or probably related to the study medication.

According to the schedule of visits in the protocol, no laboratory assessments, physical exams, or other procedures are planned after the subject's permanent discontinuation of study medication, also known as EOT; however, AE and rescue therapy assessments, including monitoring for MACE endpoints, will continue until a subject's EOS.

The analysis time periods for efficacy divide the Correction/Conversion and Maintenance periods, Year 1 collectively, into four windows (see [Table 1](#)).

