7.5.5.4 Procedures to Support Continued Study Participation

As part of the informed consent process, only subjects who fully understand and agree to full participation and long-term follow-up should be consented to participate. **It is important that subjects understand the long-term duration and purpose of a cardiovascular outcome trial and that the subject (or designee) continue to allow follow-up through global study completion which could be several years, even post subject's permanent discontinuation of study medication.**

In all cases of impending study medication discontinuation or subject request for stopping study visits, the Investigator will discuss with the subject their options of continuing in the study.

It is important to continue to follow every randomized subject, even if discontinued study medication, through global study completion at a frequency and approach that is agreed to between the Investigator and subject. Visit schedule and assessments are flexible and at the discretion of the Investigator and subject and will be clearly documented in the medical chart. Optimal data collection would include the following assessments through global study completion:

- EOS subject status (must collect at minimum)
- MACE Endpoint Questionnaire
- AE Assessment

The protocol allows flexibility of follow-up to maintain the subjects in active status post permanent discontinuation of study medication. For those subjects who decline full participation in the study post discontinuation of study medication, other options for continued follow-up on a subject include (but are not limited to):

1. Reduced frequency of on-site visits
2. Telephone visits in lieu of on-site visits
3. Telephone or any contact method (e.g., email, site staff visit subject's home, etc.) to verify vital status
4. Telephone or any contact method with an alternative person (family member or medical designee)
5. Study team access to medical records for reporting MACE data or vital status

In the most extreme case, the protocol will accommodate minimal contact with a subject or alternative method to obtain the subject's vital status. The objective is to **keep a subject's study status active** to ascertain at a minimum vital status (alive or deceased) at the global study completion.

The Investigator will ensure understanding and documentation of the reason(s) for a subject's desire to stop study procedures or stop study medication.

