9.3.10 Follow-Up Visit

The Follow-up visit will be conducted in person or via the telephone 4 weeks after the EOT visit. The following activities/procedures will be performed:

- AE assessment
- RBC transfusions and ESA rescue
- Therapeutic phlebotomy
- MACE endpoint questionnaire.
- Recording of concomitant medications

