If new elevations in ALT or AST > 3 times ULN, **without** an elevation of total serum bilirubin >2 times ULN are identified, the following steps are to be taken:

- Temporary discontinuation of Investigational Medicinal Product (IMP);
- Repeat testing of ALT, AST, ALP, and total bilirubin, should be completed within 48 to 72 hours to confirm the abnormalities and to determine trend;
- IMP should not be resumed until monitoring indicates abnormalities have resolved or have stabilized.

Details on the management of subjects with other ALT and AST abnormalities are further described in [Section 9.4, Study Medication Stopping Rules](#).

Worsening of Anemia – In this study, it is possible that some subjects may experience a worsening of anemia. As the primary endpoint of this study assesses Hb response, worsening of anemia is captured as part of this efficacy parameter. Worsening of anemia should not be considered an AE unless the worsening of anemia is associated with a cause *other than* the subject's CKD.

Transplantation – During this long-term study, it is anticipated that some subjects may receive a kidney transplant. These events will not be recorded as AEs. Subjects will discontinue study medication for receipt of a kidney, other solid organ, hematopoietic stem cell or bone marrow transplant and should continue with the Schedule of Activities and safety assessments as described in [Section 7.5.5.2, Permanent Discontinuation of Study Medication](#).

Malignancy – During this long-term study, some subjects may develop a newly diagnosed malignancy or a recurrence of a malignancy. At the discretion of the Investigator, these subjects may continue study medication (vadadustat or darbepoetin alfa). For reporting of adverse events of malignancy, see [Section 10.1.2 Serious Adverse Events](#).

Renal-Related Events - Some subjects will experience a progression of their CKD over the course of this study as part of the natural course of the disease. In addition, the study population is prone to experience acute, transient loss of kidney function of different etiologies, sometimes concomitantly complicated by progression of CKD.

To ensure consistent reporting of renal events, the following guidelines are to be used when reporting a renal-related AE:

- The following situations **should always be reported as SAEs** with seriousness criterion “medically important,” if no other seriousness criteria are met (see Section 10.1.2, Serious Adverse Events):

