11.5 Missing Data

Subjects who stop study medication treatment after randomization and prior to completion of the study should continue with planned study visits and assessments unless they withdraw consent for participation in the study. Similarly, subjects will continue with study medication and study procedures following the initiation of rescue therapy, with the exception that the subjects must discontinue taking study medication while receiving an ESA rescue therapy. Treatment with study medication should be resumed after an appropriate interval following the ESA rescue therapy as described in [Section 8.4.7, Rescue Therapy](#). Data will continue to be collected following initiation of the rescue therapy as per the study Schedule of Activities.

All data collected during the study, including at any point after the initiation of rescue therapy as well as after early discontinuation of study medication treatment, will be used for the primary analysis as well as main analyses of all efficacy endpoints. Sensitivity analyses will be performed to assess an impact of rescue therapy on study conclusions.

In the primary analysis of the primary efficacy endpoint, all available qualifying Hb measurements during the pretreatment period and during the primary evaluation period (Weeks 24-36) will be used to calculate an average Hb during each period respectively, for each subject. For any subject with no available Hb measurements during the primary evaluation period, multiple imputation will be used to impute a change from Baseline value (details are provided in the SAP). In an analogous manner, an average Hb will be calculated for the secondary evaluation period (Weeks 40-52) for each subject. Given the design of this study where the subjects will continue to be assessed after early study medication discontinuation, it is expected that there will be only a minimal amount of missing data and the primary analysis should not be substantially affected by the imputation.

All data pertaining to the MACE endpoint collected at any point during the study, both during study medication treatment and post study medication treatment discontinuation, and regardless of the rescue therapy, will be used for the primary analysis of the MACE endpoint and its individual components.

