Abbreviations: AE = adverse event; ALT/SGPT = alanine aminotransferase/serum glutamic-pyruvic transaminase; AST/SGOT = aspartate aminotransferase/serum glutamic oxaloacetic transaminase; BUN = blood urea nitrogen; CBC = complete blood count; CPK = creatine phosphokinase; CRF = case report form; diff = differential; ECG = electrocardiogram; eGFR = estimated glomerular filtration rate; EOT = end of treatment; ESA = erythropoiesis-stimulating agent; HDL = high density lipoprotein; Hb = hemoglobin; HIF = hypoxia inducible factor; ICF = informed consent form; I/E = inclusion/exclusion; INR = international normalized ratio; IWR = interactive web response; LDH = lactate dehydrogenase; LDL = low density lipoprotein; MACE = major adverse cardiovascular event; MCH = mean corpuscular hemoglobin; MCHC = mean corpuscular hemoglobin concentration; MCV = mean corpuscular volume; med = medication; PK = pharmacokinetic; PS = Pre-Screening; PT = prothrombin time; PTT = partial thromboplastin time; RBC = red blood cell; RDW = red cell distribution width; SV1 = Screening visit 1; SV2 = Screening visit 2; TIBC = total iron binding capacity; Trtmt = treatment; TSAT = transferrin saturation; uACR = urine albumin to creatinine ratio; VEGF = vascular endothelial growth factor; WBC = white blood cell; wks = weeks.

- [a] The Screening period is a maximum of 8 weeks in duration. The Baseline visit must be performed at a minimum of 4 days from the last Screening visit (SV2), or date of last re-test.
- [b] The Follow-up visit can be performed either in person OR via the telephone.
- [c] The EOT visit will be performed at the time a subject permanently discontinues study medication (vadadustat or darbepoetin alfa) or for subjects on study medication at the time of notification of global study completion. It is important to continue to follow subjects that discontinue study medication through global study completion at a frequency and approach that is agreed to between the Investigator and subject. Visit schedule and assessments are flexible and at the discretion of the investigator and subject and will be clearly documented in the medical chart.

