- [d] An abbreviated ICF will be used for Pre-Screening. If the subject is eligible for Screening, a separate full ICF will be used, which may be signed in advance of the SV1 procedures. The Screening period starts at the time the informed consent is signed and will be a maximum of 8 weeks in duration. An optional consent form for collection of blood samples for future genetic analysis will be provided at SV1. An additional optional consent form for participation in an adrenal function substudy in 200 subjects in the EU will also be provided at SV1.
- [e] If the Pre-Screen HemoCue Hb is between 8.0 and 11.0 g/dL (inclusive) within the US or between 9.0 and 12.0 g/dL (inclusive) outside of the US, the investigative site may proceed with Screening Visit 1 (SV1), preferably on the same day as Pre-Screening.
- [f] Inclusion/Exclusion criteria will be reviewed at the Pre-Screening and Screening visits (SV1 and SV2). Final eligibility determination will occur following the Screening visits when all data are available.
- [g] Vitals: Heart rate and blood pressure to be assessed in the seated position after 5 minutes of rest. Height (SV2 only) and weight (SV2, Weeks 12, 24, 36, and 52, yearly thereafter, and at the EOT visit) will also be measured.
- [h] Physical exam: a physical exam is required at SV2 as outlined in the protocol. Thereafter, an abbreviated symptom-directed physical exam should be performed at the discretion of the Investigator as clinically indicated.
- [i] ECG should be performed prior to blood draws when possible and obtained after the subject has been resting comfortably in a supine position for approximately 5 minutes.
- [j] Serum pregnancy will be tested in women of childbearing potential at SV2. (Eligible subjects will be advised to use an adequate contraceptive method.) Additional serum or local urine pregnancy tests should be conducted throughout the study in sufficient number, as determined by the Investigator or required by local regulations, to establish the absence of pregnancy during the study. If positive at SV2, the subject is not eligible to enter the study. If a subject becomes pregnant during the study, the subject must permanently discontinue study medication and should attend all subsequent study visits and be continually monitored according to the Schedule of Activities for the duration of the study.
- [k] Subjects may be retested and/or rescreened as detailed in [Section 7.4 Retesting and Rescreening](#)

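### Protocol and SAP disagree on whether hemoglobin is collected after study drug is stopped, and the planned imputation cannot fill that gap for a treatment-policy estimand

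*SAP*

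**What the plan says.** **Protocol, Amendment 7-COL**

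- Section 11.5: subjects who stop drug "should continue with planned study visits and assessments unless they withdraw consent for participation in the study". For that reason it expects that "there will be only a minimal amount of missing data and the primary analysis should not be substantially affected by the imputation". Sections 11.5 and 11.6.1.1 use Hb collected after discontinuation in the primary analysis.
- Section 7.5.5.2 places the EOT visit at permanent discontinuation and returns the subject to standard care, which may include an ESA.
- Section 7.5.5.4: "Visit schedule and assessments are flexible and at the discretion of the Investigator and subject". Appendix A footnote [c] repeats this. The list of what would ideally be collected (also in Section 7.5.2) is end-of-study status, the MACE questionnaire and adverse events. It contains no Hb.
- Section 9.3.10: "The Follow-up visit will be conducted in person or via the telephone 4 weeks after the EOT visit". It lists no laboratory test.
- Two texts point the other way. After transplant (Section 10.1.1), subjects "should continue with the Schedule of Activities and safety assessments as described in" Section 7.5.5.2. After pregnancy (Appendix A footnote [j]), they "should attend all subsequent study visits and be continually monitored according to the Schedule of Activities for the duration of the study".

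**SAP**

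- Section 2.2: under the protocol's visit schedule, "no laboratory assessments, physical exams, or other procedures are planned after" permanent discontinuation. Adverse event, rescue and MACE follow-up continue.
- Section 9.1.4 sets a treatment-policy estimand in the randomized population. Sections 5.1 and 9.1.2 use any central-laboratory Hb that falls in the window, whatever the subject's disposition.
- Section 9.1.5 has a sensitivity analysis that sets Hb after EOT to missing. Appendix C.1.2 describes the same analysis without the EOT clause.
- Appendix B imputes separately by arm under MAR.

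**The concern.** A treatment-policy estimate needs Hb measured after subjects stop drug, or a credible model for it. The protocol's statistics section assumes the measurements will exist. The SAP says none are planned, and the protocol's own operating instructions for stoppers do not ask for them. Unless this is settled, sites may not draw the blood, and the imputation will fill the gap with values learned mostly from subjects still on drug.

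The result would then drift toward Hb as if treatment had continued while being reported as Hb regardless of discontinuation. The error can go either way: Hb may fall after stopping, or rise if an ESA is resumed.

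**Working it through.** **1. The plan's own power figure.** SAP 2.7 gives SD 1.5 g/dL, 925 per arm, margin -0.75, true difference 0 and power above 90%. SE = 1.5 × √(2/925) = 0.0697. The 95% half-width is 1.96 × 0.0697 = 0.137. Power = Φ(0.75/0.0697 − 1.96) = Φ(8.8), effectively 100%. About 85 per arm would give 90%. The stated figure is met with much to spare, so the issue is bias and not precision.

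**2. Who lacks data.** SAP Table 1 opens the primary window on Study Day 155. On the SAP 2.2 reading, a subject who stops before then generally has no Hb in it. One who stops inside it contributes Hb only up to the EOT visit.

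**3. What the imputation knows.** Table B 1 and Exhibit B 1 include the subject's own baseline, Weeks 2-8 and Weeks 10-20 Hb, and the EOT blood count enters these by date. They also include other laboratory values and baseline factors. The ESA variable is baseline dose only. There is no variable for discontinuation, time off drug or post-baseline ESA.

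**4. Size of the error.** Let d be the share of an arm missing after stopping, and g the imputed minus the actual mean Hb among them, after conditioning on their earlier Hb.

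Error in the difference = d_v·g_v − d_c·g_c (v vadadustat, c darbepoetin).

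The documents give neither d nor g, so every value below is assumed.

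| d_v, d_c | g_v, g_c (g/dL) | Error (g/dL) | Share of 0.75 |
|---|---|---|---|
| 20%, 15% | 0.5, 0.5 | 0.100 − 0.075 = +0.025 | 3% |
| 25%, 15% | 0.75, 0.75 | 0.1875 − 0.1125 = +0.075 | 10% |
| 25%, 15% | 1.0, 0.3 | 0.250 − 0.045 = +0.205 | 27% |
| 25%, 15% | −0.5, −0.5 | −0.125 + 0.075 = −0.050 | 7% |
| 25%, 15% | −0.5, +0.3 | −0.125 − 0.045 = −0.170 | 23% |
| equal | equal | 0 | 0% |

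Positive errors favor vadadustat.

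**5. Does conditioning on earlier Hb remove it?** A simulation used one million subjects per arm with true difference 0. Assumed SDs were 0.9 to 1.2 and correlations 0.3 to 0.6. Stopping (25% v 15%) was driven by low Weeks 10-20 Hb.

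- No change after stopping: complete-case error 0.067, MAR imputation error 0.002. A low Hb at the time of stopping is handled.
- Change after stopping of −0.5 in both arms: +0.050. Of −1.0 v −0.3: +0.204. Of +0.5 v −0.3: −0.169. The change after stopping passes through almost in full.

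**6. What measurement buys.** A second simulation assumed 30% stopping in each arm and an off-drug change of −1.0 g/dL on vadadustat only, so the true difference is −0.30. With no Hb after EOT, MAR imputation returned 0.00. With 30% of stoppers still measured it returned −0.11 without a discontinuation term and −0.30 with one.

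**7. Shift needed to lose non-inferiority.** With 20% v 15% missing, SE on observed subjects = 1.5 × √(1/740 + 1/786.25) = 0.0768. For a MAR estimate E, the tolerated shift among vadadustat stoppers is (E + 0.75 − 1.96 × 0.0768)/0.20. If darbepoetin stoppers' actual Hb is 0.5 above imputed, subtract 0.15 × 0.5 = 0.075 from the numerator.

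| E | Darbepoetin at MAR | Darbepoetin stoppers +0.5 |
|---|---|---|
| 0 | 3.00 | 2.62 |
| −0.3 | 1.50 | 1.12 |
| −0.5 | 0.50 | 0.12 |

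**8. Superiority.** SAP 2.7 and 9.1.4 declare superiority if the lower limit exceeds zero. With 25% v 15% missing, SE = 1.5 × √(1/693.75 + 1/786.25) = 0.078 and the half-width is 0.153. The +0.205 case alone would put the expected lower limit at about +0.05 when the true difference is zero.

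**The case against.** SAP 2.2 describes a schedule; it is not a collection instruction, and the rule that the SAP prevails covers analyses only. Sites follow the protocol, and Section 7.5.5.4 offers reduced contact to subjects who decline full participation, which suggests full participation is the default. The transplant text refers back to Section 7.5.5.2, so it is weak evidence of a separate rule. All this softens the conflict without settling it: no list of assessments for stoppers, including the ideal one, names Hb.

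The tipping-point analysis in Appendix B.3.2 already lowers imputed vadadustat Hb until non-inferiority fails. Shifting all missing vadadustat values is at least as severe as shifting discontinuers only. That stands for the downward vadadustat direction. The analysis does not move darbepoetin off MAR, does not look upward and does not identify discontinuers. The other planned analyses do not fill the gap: MMRM again relies on MAR, the per-protocol set requires drug in the window, and the rescue/EOT analysis discards off-drug Hb.

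All shares and shifts are assumed, the protocol expects little missing data, and the larger errors need both an imbalance between arms and unequal changes. That is true and limits the claim. At 10% missing and an estimate of zero, the tolerated vadadustat shift is about 6.1 g/dL.

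An imputation based on off-treatment Hb may lack data, so a fallback is needed. The current protocol in the file is specific to Colombia, so the wording used elsewhere cannot be seen. Both points stand.

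**Conclusion.** The concern holds and should be fixed before unblinding. The two documents, and the protocol within itself, disagree on whether Hb is collected after permanent discontinuation. If it is not, within-arm MAR imputation with no discontinuation term does not reliably target the treatment-policy estimand.

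Under the assumed shares and changes the error runs from −0.17 to +0.21 g/dL. It vanishes if off-drug Hb matches the imputation or the effects cancel between arms. The non-inferiority conclusion is at risk only if the estimate is already near the margin, for example around −0.5 g/dL. Confidence in the size is medium, because the documents supply neither discontinuation rates nor off-drug Hb changes.

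**What to change.** 1. **Reconcile the texts.** Align protocol 11.5, 7.5.5.4, 10.1.1 and Appendix A footnotes [c] and [j] with SAP 2.2. Name the already scheduled central-laboratory blood counts at Weeks 24-36 and 40-52 among the assessments to keep for subjects who stopped drug and still attend. Make SAP 9.1.5 and Appendix C.1.2 agree on whether Hb after EOT is set to missing.
2. **Add one sensitivity analysis to SAP Appendix B, leaving the primary analysis unchanged.** Impute Hb missing after discontinuation from off-treatment Hb in the same arm, with time since EOT and resumed ESA as predictors, provided a minimum number fixed before unblinding is available. Otherwise apply the tipping-point shift to discontinued subjects only, separately in each arm and in both directions. Report it beside the primary result.
3. **Report the missingness.** Tabulate subjects with no Weeks 24-36 Hb by arm and discontinuation status, and delete or qualify the protocol's expectation of minimal missing data. Keep treatment policy as the target and state MAR as the assumption used for missing values.

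Items 2 and 3 cost SAP wording, one table and extra imputation runs. Item 1 keeps up to four scheduled draws per window for stoppers who attend; as a protocol change it may need approval under Section 15.2.
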